# Vapotherm, Inc

## MODERATION Neo – Maintaining Optimal DEliveRy Using Automatic TItration of OxygeN Neonatal

Confidential

- FiO2 fluctuations compared to manual control
  - Coefficient of variance for FiO2 for the study arm
  - Standard deviation of FiO2 for the study arm
- Index of overshoot (an elevated SpO2 resulting from the FiO2 titration response to a low SpO2) and characterization of such excursions.
  - The proportion of time, number of episodes, and average duration per episode of Overshoot, defined as SpO2 > range following SpO2 < range for ≥10 seconds duration.
  - The proportion of time, number of episodes, and average duration per episode of Overshoot, defined as SpO2 > range for 70s following SpO2 < range.
- Number of Episodes of hypoxia (below range) within 60-180s after a return to FiO2=0.21.
- Number of Episodes of hypoxia (below range) within 60-180s after a return to FiO2=0.21 followed by hyperoxia (above range) within 60-180s after a return to FiO2=0.21.
- The mean FiO2 of the study arms
- Number of overall adjustments (or adjustments/hour) to FiO2 in manual mode compared to automated control.
- The care ratio (i.e., Nurse:Baby) will be recorded, patients will be separated to care ratio, and each care ratio group will be compared between study arms for the proportion of time, number of episodes, and average duration of episodes
  - SpO2 in target range
  - SpO2 below target range
  - SpO2 below 80% for episodes ≥60s
  - SpO2 below 80%
  - SpO2 below 70%
  - SpO2 in 80% to 86% range
  - SpO2 above target range at FiO2>0.21 (not at air)
  - SpO2 in target range at FiO2=0.21
  - SpO2 above 98% at FiO2>0.21
  - SpO2 below target range at FiO2=0.21
- Comparison between Day versus Evening/Ovenight of the Proportion of Time, Number of Episodes, and Average Duration of Episodes in target, high, and low SpO2 ranges (with or without FiO2 at or above 21%)
  - SpO2 in target range
  - SpO2 below target range
  - SpO2 below 80% for episodes ≥60s
  - SpO2 below 80%
  - SpO2 below 70%
  - SpO2 in 80% to 86% range
  - SpO2 above target range at FiO2>0.21 (not at air)
  - SpO2 in target range at FiO2=0.21
  - SpO2 above 98% at FiO2>0.21
  - SpO2 below target range at FiO2=0.21

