# Vapotherm, Inc

## MODERATION Neo – Maintaining Optimal DEliveRy Using Automatic TItration of OxygeN Neonatal

Confidential

- SpO2 below target range at FiO2=0.21
- Number of manual adjustments to FiO2 in manual mode compared to automated control (manual override).
- Proportion of Time at or below FiO2 ranges compared between study arms
  - FiO2 at 0.21 (air)
  - FiO2 below 0.25
- SpO2 fluctuations auto compared to manual control
  - Coefficient of variance for SpO2 for the study arm
  - Standard deviation of SpO2 for the study arm
- FiO2 fluctuations Auto compared to manual control
  - Coefficient of variance for FiO2 for the study arm
  - Standard deviation of FiO2 for the study arm
- Index of overshoot (an elevated SpO2 resulting from the FiO2 titration response to a low SpO2) and characterization of such excursions.
  - The proportion of time, number of episodes, and average duration per episode of Overshoot, defined as SpO2 > range following SpO2 < range for ≥10 seconds duration.
  - The proportion of time, number of episodes, and average duration per episode of Overshoot, defined as SpO2 > range for 70s following SpO2 < range.
- Number of Episodes of hypoxia (below range) within 60-180s after a return to FiO2=0.21 compared between arms.
- Number of Episodes of hypoxia (below range) within 60-180s after a return to FiO2=0.21 followed by hyperoxia (above range) within 60-180s after a return to FiO2=0.21 compared between arms.
- The mean FiO2 of the study arms
- Number of overall adjustments (or adjustments/hour) to FiO2 in manual mode compared to automated control.
- The care ratio (i.e., Nurse:Baby) will be recorded, patients will be separated to care ratio, and each care ratio group will be compared between study arms for the proportion of time, number of episodes, and average duration of episodes
  - SpO2 in target range
  - SpO2 below target range
  - SpO2 below 80% for episodes ≥60s
  - SpO2 below 80%
  - SpO2 below 70%
  - SpO2 in 80% to 86% range
  - SpO2 above target range at FiO2>0.21 (not at air)
  - SpO2 in target range at FiO2=0.21

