## **Additional Analyses**

These exploratory analyses will use descriptive statistics to quantify values in each arm and the difference (OAM – standard practice). These analyses will use the mITT and PP populations except for adverse event summaries

To quantify and compare OAM automatic mode to standard manual practice performance with additional measures including:

- Proportion of Time, Number of Episodes, and Average Duration of Episodes in both high and low SpO2 ranges (with or without FiO2 at or above 21%)
  - SpO2 below target range
  - SpO2 below 80% for episodes  $\geq 60$ s
  - SpO2 below 80%
  - SpO2 above target range at FiO2>0.21 (not at air)
  - SpO2 below 70%
  - SpO2 in 80% to 86% range
  - SpO2 in target range at FiO2=0.21
  - SpO2 above 98% at FiO2>0.21 (not at air)
  - SpO2 below target range at FiO2=0.21
- Number of manual adjustments to FiO2 in manual mode compared to automated control (manual override).
- Proportion of Time at or below FiO2 ranges compared between study arms
  - FiO2 at 0.21 (air)
  - FiO2 below 0.25
- SpO2 fluctuations compared to manual control
  - Coefficient of variance for SpO2 for the study arm
  - Standard deviation of SpO2 for the study arm

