### *Automated data collection*

Data logged by the data collection module(s) will be abstracted to produce total counts of events per recording period, normalized and presented per-hour, the 24-hour average, as well as hourly median/mean/stdev/min/max SpO2 and FiO2 values for trending.

Data logged by the data collection module(s) will be abstracted and analyzed for the following parameters:

Index	Mean ± SD	Proportion of total time spent	Episodes of occurrence	Duration of Episodes
SpO 2 within range		X		
SpO 2 coefficient of variance	X			
SpO 2 within range (any FiO 2 ) and between 90-100% whilst FiO 2 at 0.21		X	X	X
SpO 2 > range	X		X	X
SpO 2 > range w/ FiO 2 > 0.21	X		X	X
SpO 2 > 98%	X		X	X
SpO 2 > 98% w/ FiO 2 > 0.21	X		X	X
SpO 2 < range	X		X	X
SpO 2 in 80% to 86% range	X		X	X
SpO 2 < 80%	X		X	X
SpO 2 <80% for ≥ 60 sec	X		X	X
SpO 2 < 70%	X		X	X
Overshoot: SpO 2 > range following SpO 2 < range ≥10 seconds duration		X	X	X
Overshoot: SpO 2 > range for 70 sec following SpO 2 < range		X	X	X
Time with FiO 2 at 0.21	X			
Time with FiO 2 < 0.25	X			
FiO 2 adjustments: Manual & Auto	X			
Night/Day: SpO 2 within range		X	X	X

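### The frequency of overshoot, and of hypoxia after a return to room air, is compared between arms only as time share or counts, with no rate per opportunity

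*Combined protocol and SAP*

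**What the plan says.** The index of overshoot is listed in section II (Additional Objectives) and again in section V (Additional Analyses). It is described as "an elevated SpO 2 resulting from the FiO 2 titration response to a low SpO 2", which is a statement about what happens after a low. Two definitions follow, one with a 10-second criterion and one with a 70-second criterion. Each is summarised by "The proportion of time, number of episodes, and average duration per episode of Overshoot".

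Both sections then list "Number of Episodes of hypoxia (below range) within 60-180s after a return to" FiO2 0.21. A companion count covers such hypoxia followed by hyperoxia.

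Section VII (Automated data collection) says logged data are "abstracted to produce total counts of events per recording period, normalized and presented per-hour", so the only denominator for counts is recording time.

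Two related outputs appear on separate lines of Additional Analyses. One is the "Proportion of Time, Number of Episodes, and Average Duration of Episodes in both high and low" SpO2 ranges, which includes episodes below target range. The other is the proportion of time at FiO2 0.21. The number of returns to 0.21 is not listed.

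The status of all this is stated plainly: "These exploratory analyses will use descriptive statistics to quantify values in each arm and the difference".

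**The concern.** An overshoot can occur only after a low, and hypoxia after a return to air only after a return. If the arms differ in the number of lows or returns, their counts will differ even when the FiO2 response to each one is equally good. Dividing by hours corrects for unequal recording length but not for unequal opportunity. The share of time spent in overshoot has the same property, because it is the count times the mean duration divided by recording time.

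This matters because the plan's own pilot data lead one to expect much less time below range under OAM. A lower overshoot count under OAM could mean fewer lows, better titration after each low, or both, and the planned summaries would not separate these. The index is described as a property of the titration response, so the reader will want that separation.

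**Working it through.** **Inputs.** Time below range comes from section V, Sample Size Calculations: Table 1 (infants of 1000 g or more, N = 18) and Table 2 (by weight). Arm length is 24 hours (section IV). The documents give no count, rate or duration of low episodes, overshoots or returns to 0.21, so there is no stated figure on this point to reproduce.

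**Table check.** The Table 1 difference agrees with its arm means: 14.4 − 27.0 = −12.6.

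**Identities.**
- Overshoot count = number of low episodes × probability of overshoot per low episode.
- Number of low episodes = time below range ÷ mean low-episode duration.
- Post-return hypoxia count = number of returns to 0.21 × risk per return.

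**Time below range, OAM/manual.**
- Table 1: 14.4/27.0 = 0.53. In hours per 24-hour arm: 0.144 × 24 = 3.46 against 0.270 × 24 = 6.48.
- Table 2, lighter group: 15.3/28.7 = 0.53. Heavier group: 13.1/24.4 = 0.54.

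**Overshoot count ratio at equal risk per low.** This equals the low-episode ratio, 0.533 ÷ (OAM/manual ratio of mean low-episode duration). The duration ratio is an assumption.

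| Assumed duration ratio | Low-episode ratio = overshoot count ratio |
|---|---|
| 0.5 | 1.07 |
| 0.75 | 0.71 |
| 1.0 | 0.53 |
| 1.5 | 0.36 |
| 2.0 | 0.27 |

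In every row the ratio per low episode is 1.00. With equal durations, the count comparison would show a fall of 1 − 0.53 = 47% with no difference in response. The risk per low under OAM would have to be 27.0/14.4 = 1.875 times the manual risk before the counts were equal.

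**Hypoxia after a return to 0.21.** At equal risk per return, the count ratio equals the ratio of returns. That ratio is neither given nor among the planned outputs, so no figure follows.

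**Limit of the inputs.** The Table 1 means for in, above and below range sum to 76.0 + 13.5 + 14.4 = 103.9 (OAM) and 47.6 + 28.5 + 27.0 = 103.1 (manual). The categories seem to overlap, so 0.53 is approximate.

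**The case against.** The case for leaving the plan alone has several parts.

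**Burden per infant is a legitimate estimand.** It keeps the randomised comparison intact. A ratio per low conditions on something that happens after randomisation: if OAM averts the milder lows, those that remain differ in kind. This stands, and it is why the ratio should be added beside the counts and not replace them.

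**The plan measures over-correction and weaning elsewhere.** A reader might infer that these are its only such measures. They are not. Time above and time below range are the primary safety endpoints. Additional Analyses also covers high SpO2 while FiO2 exceeds 0.21, low SpO2 at 0.21, and the variability of SpO2 and FiO2. What remains is that none of these is a rate per opportunity.

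**Not every listed measure scales with opportunity.** Average duration per overshoot does not. However, it describes overshoots that have occurred and does not say how often one follows a low.

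**Low-episode counts are already reported.** A rough ratio could therefore be formed for overshoot. But the default episode in section VII lasts at least 5 seconds, while the first overshoot definition carries a 10-second criterion, so numerator and denominator may not match. For returns to 0.21, no listed output supplies a denominator.

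**The overshoot definition is not as loose as it may look.** A reader might infer that any later high counts, including one after spontaneous recovery on air. Section V defines the target range at FiO2 0.21 as 90–100% for all analyses, so a high on room air is not above range. The heading also ties the high to the titration response. What remains is that the first definition states no time window, and the 70 seconds in the second can be read as a window or as a duration.

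**Conclusion.** The point holds as a gap in exploratory reporting. The frequency of overshoot and of post-return hypoxia is planned only as time share or counts, so opportunity and response cannot be separated from the listed outputs.

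For overshoot, equal risk per low would give a count ratio of about 0.53 if low episodes last equally long in both arms. The range is 1.07 to 0.27 for duration ratios of 0.5 to 2.0. All of this rests on approximate pilot time below range and an assumed duration ratio.

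A reader might go further and infer that the overshoot comparison mostly reflects the number of lows, or is biased towards OAM. The documents do not show that. If OAM halves the length of lows, the distortion nearly vanishes and slightly reverses. Nor do they support saying that post-return hypoxia counts are biased against OAM because a controller returns to air more often: the number of returns is unknown, so direction and size are too.

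The consequence is limited to how these descriptive results can be interpreted. No primary or secondary test, alpha or sample size changes.

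**What to change.** In Additional Objectives, Additional Analyses and the Automated data collection table, make these changes for each infant and arm:

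1. Add overshoot episodes per qualifying low episode, applying to the low the same duration criterion as the overshoot definition uses.
2. Add hypoxia episodes per return to FiO2 0.21.
3. Report both denominators: the number of qualifying lows and the number of returns. An infant with none in an arm has no ratio, and this should be visible.
4. Keep the existing time shares and per-hour counts, labelled as burden measures.
5. State the time window that links the low to the high, whether the 70 seconds is a window or a duration, and whether the 10 seconds applies to the low or the high.

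A version restricted to lows followed by an FiO2 increase may be added as a sensitivity summary, but it need not be the main definition.

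The cost is a few lines of text and programming. SpO2 and FiO2 are already logged every second in both arms (section IV), so no new data are needed. The downside is slightly more descriptive output, and the ratios condition on a post-randomisation event and should be presented with that caveat.

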# Vapotherm, Inc

## MODERATION Neo – Maintaining Optimal DEliveRy Using Automatic TItration of OxygeN Neonatal

Confidential

- CONSORT Diagram will be used to articulate the patient numbers
- For each arm of the study will aggregate the proportion of time for SpO2 for data bins from <80% to 100%.
- For each arm of the study will aggregate the proportion of time for FiO2 for data bins 0.21 to 1.0.
- Adverse events as reported on the CRFs (Summarized by seriousness and relatedness to therapy) – See Appendix B for the list of adverse events and classification criteria.

### Sample Size Calculations

The sample size was initially based upon data from the Reynolds trial looking at a subset of subjects expected to be enrolled in this trial (enrollment weight initially 1000g-2500g, now 1000g – 3500g). These data are presented in Tables 1 and 2 below. While we are requesting with this IDE Study to now enroll larger babies, the Study sample size will not be changing.

**Table 1. Summary of unpublished Reynolds data for infants with enrollment weight 1000g or greater.**

SpO2 % time	N	Auto (OAM)			Manual (Standard Practice)			Difference		
		Mean	SD	Median	Mean	SD	Median	Mean	SD	Median
In range	18	76.0	12.3	79.1	47.6	14.0	50.4	28.4	10.8	27.1
Above	18	13.5	5.7	12.4	28.5	17.5	23.4	-15.0	16.2	-10.0
Below	18	14.4	7.1	12.6	27.0	8.9	27.4	-12.6	10.8	-11.5

**Table 2. Summary of unpublished Reynolds data for infants by weight category.**

Weight	SpO2 % time	N	Auto (OAM)			Manual (Standard Practice)			Difference		
			Mean	SD	Median	Mean	SD	Median	Mean	SD	Median
1000-1500g	In range	11	74.4	11.3	77.0	47.4	11.9	50.2	26.9	6.5	26.4
	Above	11	14.2	5.4	13.6	26.8	15.1	23.3	-12.6	12.6	-10.2
	Below	11	15.3	6.6	13.9	28.7	9.5	29.4	-13.4	11.3	-14.5
1500g-2500g	In range	7	78.5	14.1	83.2	47.8	17.8	52.1	30.7	15.8	27.1
	Above	7	12.3	6.5	9.5	31.2	21.6	29.0	-18.9	21.3	-8.9
	Below	7	13.1	8.1	10.5	24.4	7.8	22.4	-11.3	10.8	-10.0

For sample size calculations comparing the difference of values in the same subject, the sample size is driven by the standard deviation. We will identify what difference the trial is powered to detect with the specified sample size and standard deviation.

#### *Safety co-Endpoints – Time Above Target Range and Below Target Range:*

The safety co-endpoints will be powered to detect superiority even though we will first test for non-inferiority. The change in proportion of time SpO2 was above and below range was

# Vapotherm, Inc

## MODERATION Neo – Maintaining Optimal DEliveRy Using Automatic TItration of OxygeN Neonatal

Confidential

$-15.0\% \pm 16.2\%$  and  $-12.6\% \pm 10.8\%$ , respectively. Using the largest standard deviation of 16%, again using PASS 14, a sample size of 38 will be adequate with at least 95% power for each test with a one-sided alpha of 0.025 to detect a difference as small as 10%. Both safety endpoints are powered at 95% ensure overall power is at least 90%.

### *Primary Performance Endpoint – Time in Target Range:*

The change in proportion time SpO2 was in target range is  $28.4\% \pm 10.8\%$ . Rounding the standard deviation up to 11, using PASS 14 test for paired means with a nonparametric adjustment, a two-sided alpha of 0.05, with at least 90% power, a sample size of 40 will detect a difference from zero with a mean change as small as 6%. Our expected difference far exceeds this amount.

### *Secondary Performance Endpoint 1 – Time in Target Range by weight subgroup:*

For the secondary performance endpoint (weight stratification subgroups of primary performance endpoint), using the maximum standard deviation from the Reynolds data, a standard deviation of 15.8% will be rounded to 16% for sample size calculations. Using PASS 14, with a two-sided alpha of 0.05 and at least 90% power, a standard deviation of 16, the sample size of 17 subjects per weight stratification will be adequate to detect differences as small as 14% for time in range with adequate power.

### *Secondary Performance Endpoint 2 – Time in Target Range by skin pigmentation:*

For the secondary performance endpoint (stratification subgroups of primary performance endpoint by skin pigmentation [light or dark]) pilot data are unavailable by skin pigmentation, but we will assume the performance is similar to the maximum standard deviation from the Reynolds data, a standard deviation of 15.8% will be rounded to 16% for sample size calculations. Using PASS 14, with a two-sided alpha of 0.05 and at least 90% power, a standard deviation of 16, the sample size of 17 subjects per skin pigmentation stratification (light or dark) will be adequate to detect differences as small as 14% for time in range with adequate power.

Overall sample size will be driven by goal of at least 17 subjects per weight group and an overall sample size of at least 40 subjects per the primary performance endpoint. Allowing up to 15% attrition, expected enrollment will be 47 subjects.

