### **Poolability**

A poolability analysis will be performed to assess the poolability of sites with respect to the primary performance endpoint measure in the mITT subjects. A Student's t-test will be used to test for a difference in performance across sites. A significance level of 0.15 will be used to determine whether the sites are poolable. If a significant difference is found between sites, additional analyses will be done to identify factors that may be associated with this difference. Additionally, if a significant difference is observed, a random site adjusted estimate of the performance endpoint, along with 95% CI, will be provided.

Although enrollment will be monitored in an effort to strive for even allocation between sites, for purposes of the poolability analysis those sites with less than five (5) evaluable patients enrolled will be combined into a pseudo-site for purposes of analysis.

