## **VII. Data collection**

### *Manually Entered Data*

At the point of enrollment, baseline data will be recorded on the CRF, which includes:

- Weight at birth (grams)
- Weight at time of the study (grams)
- Gestational Age at birth (Weeks Days/7)
- Age at the time of the study (Days)
- Gender
- Race / Ethnicity, and Skin Pigmentation Classification
- Current FiO2
- Current HVNI flow settings (L•min)
- Diagnoses (Primary and Secondary)
- Medications
- Acuity Score
- Confirm site of SpO2 probe placement (right hand)
- Caregiver : Patient ratio

During the study, the clinical staff will record on the CRF the following:

- Time the study was started and confirm the initial arm (Automatic / manual)
- Time the study switched arms, and confirm the second arm (Automatic / manual)
- Hourly SpO2 and FiO2 readings

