### XIII. Skin Pigmentation Color Scale

# Vapotherm, Inc

## MODERATION Neo – Maintaining Optimal DEliveRy Using Automatic TItration of OxygeN Neonatal

Confidential

To provide a plausible and applicable skin pigmentation scale to this study, the Munsell System Soil Color Chart (2009 Revision, Munsell Color, Grand Rapids, Michigan), Hue 7.5YR will be utilized to describe skin pigmentation. This color scale for skin pigmentation has been previously implemented clinically, and most recently in the Foglia 2017 clinical study that evaluated pulse oximetry bias of skin pigmentation in infants with hypoxemia. Similar to Foglia 2017, and multiple pediatric/adult studies, skin pigment stratification will be classified and defined as Light or Dark skin pigment.

Specific to the Munsell Scale: Light skin pigment will be designated as values 7 and 8, Dark skin pigment will be designated as 2.5, 3, 4, and 5, and a value of 6 will be considered intermediate and not classified as either light or dark pigment.

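### The power quoted for the skin-pigmentation objective assumes 17 light and 17 dark infants, but the enrolment goal does not aim for those numbers, so that group size is not secured

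*Combined protocol and SAP*

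**What the plan says.** The Sample Size Calculations section notes for Secondary Performance Endpoint 2 that "pilot data are unavailable by skin pigmentation". It borrows the largest pilot SD (15.8, rounded to 16) and concludes that "the sample size of 17 subjects per skin pigmentation stratification (light or dark) will be adequate to detect differences as small as 14" percentage points, with two-sided alpha 0.05 and at least 90% power.

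The paragraph that fixes enrolment follows directly: "Overall sample size will be driven by goal of at least 17 subjects per weight group", together with at least 40 infants overall for the primary performance endpoint. It ends: "Allowing up to 15% attrition, expected enrollment will be 47 subjects". Pigmentation is not mentioned there.

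Section XIII defines light as Munsell values 7 and 8 and dark as 2.5 to 5, and adds that "a value of 6 will be considered intermediate and not classified as either light or dark pigment".

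Three other places bear on the point:
- Poolability describes the only enrolment balancing in the plan, which is by site: "Although enrollment will be monitored in an effort to strive for even allocation between sites".
- Section VII lists "Race / Ethnicity, and Skin Pigmentation Classification" among the data recorded at enrolment, so the class is known at that time.
- Section V makes the secondary endpoints a basis for possible labeling claims once the primary endpoints pass. Objective 2 concerns both light and dark infants, each tested at one-sided 0.025 with a Hochberg adjustment.

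**The concern.** The weight and pigmentation objectives carry the same calculation: SD 16, 14 points, 17 per group. Weight then becomes an enrolment goal and pigmentation does not. The excluded intermediate class tightens matters, because every infant with value 6 uses one of the 47 places without adding to either pigmentation group.

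At stake is the support for a potential labeling claim covering both groups. The smaller group limits that claim, and its size is left to chance. Once enrolment closes it can no longer be influenced.

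**Working it through.** **Inputs.** From Sample Size Calculations: difference δ = 14, SD σ = 16, 17 per group, at least 40 evaluable, 47 enrolled, attrition up to 15%. From Table 1: pilot mean difference in time in range 28.4, SD 10.8; the plan's primary calculation uses 11 ("Rounding the standard deviation up to 11"). From Section XIII: value 6 is in neither group. The light/dark/intermediate mix is not in the documents and is assumed below.

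**1. Reproduce the plan's figure.** Paired t-test power = P(T > t), where T is noncentral t with n − 1 degrees of freedom and noncentrality (δ/σ)√n, and t is the 0.975 quantile of central t. At n = 17 the noncentrality is (14/16) × √17 = 3.61 and t = 2.12, so power is 0.923. The smallest n giving 90% is 16 (0.905). A nonparametric inflation, which the plan names only for the primary endpoint, gives 16 × π/3 = 16.8, hence 17. The stated figure holds, conditional on 17 infants per group.

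**2. Room inside the enrolment rule.** 47 × 0.85 = 39.95, about 40 evaluable. Two groups of 17 need 34 classified infants.
- At 40 evaluable: at most 40 − 34 = 6 may be intermediate, and neither group may exceed 40 − 17 = 23.
- At 47 evaluable (no attrition): the limits are 47 − 34 = 13 and 47 − 17 = 30.

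**3. Chance of at least 17 light and at least 17 dark.** This is the multinomial probability summed over all counts with both groups at 17 or more. The mixes are assumptions.

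| Light/dark/intermediate (%) | 40 evaluable | 44 evaluable | 47 evaluable |
|---|---|---|---|
| 50/50/0 | 0.73 | 0.90 | 0.96 |
| 50/40/10 | 0.31 | 0.58 | 0.73 |
| 42.5/42.5/15 | 0.19 | 0.50 | 0.70 |
| 50/30/20 | 0.02 | 0.11 | 0.20 |

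**4. Power if a group falls short** (single group, one-sided 0.025, before Hochberg, 14 points).

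| n in group | SD 16 | SD 11 |
|---|---|---|
| 17 | 0.92 | >0.99 |
| 16 | 0.90 | >0.99 |
| 15 | 0.88 | >0.99 |
| 14 | 0.86 | 0.99 |
| 12 | 0.79 | 0.98 |
| 10 | 0.69 | 0.95 |
| 8 | 0.57 | 0.87 |

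At the pilot difference of 28.4 points with SD 16, n = 6 gives 0.93 and n = 8 gives 0.99.

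**5. Both groups.** Under Hochberg with two tests, both succeed when the larger p-value is at or below 0.025. With 17 in each group and independent tests, that has probability 0.923 × 0.923 = 0.85.

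**The case against.** The power sentence is conditional on 17 per group and is arithmetically sound. The plan nowhere promises 17 per pigmentation group, and it says openly which goals drive the sample size. Leaving a gatekept secondary subgroup analysis outside those goals can be a deliberate choice. This stands: a reader might infer that the plan contradicts itself or that its power figure is wrong, and the documents support neither reading.

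Forty evaluable infants is a floor and 15% a ceiling on attrition. The mITT cohort needs only some time on both treatments in a 48-hour study, so the evaluable number could lie nearer 47. This also stands, and is why the table in step 3 covers 40 to 47. A reader might take the low entries to mean that a shortfall is likely. They rest on assumed mixes and show only that it is possible.

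The 14-point, SD 16 case pairs about half the pilot difference with the largest pilot subgroup SD, which came from seven infants. If the pilot difference carries over, a small group still has high power: under all four assumed mixes, even at 40 evaluable, the chance of at least six in each group is 0.99 or more. It would therefore go too far to call Objective 2 underpowered. But the plan has no pilot data by pigmentation, so it cannot rely on that difference in each group, and 14 points, SD 16 and 90% are its own planning figures.

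The objection does not remove the gap itself: the group size behind the power statement is not something enrolment aims for.

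**Conclusion.** The concern holds in a limited form. The 17-per-group power figure is right as a conditional statement, but the design does not secure 17 light and 17 dark infants. Under the assumed mixes the chance of reaching both runs from 0.02 (50/30/20, 40 evaluable) to 0.96 (50/50/0, 47 evaluable). If a group ends at 15 or fewer, the stated 90% no longer applies to it at 14 points and SD 16.

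Severity is minor to moderate. The loss is small if the SD is nearer 11 or the difference nearer 28.4 points, and the primary endpoints do not depend on pigmentation. The power figures assume normally distributed paired differences; the joint figure of 0.85 also assumes that the two tests are independent. The check covers the text available for review, which has no pigmentation minimum, quota or expected mix.

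**What to change.** 1. In Sample Size Calculations, extend the goal sentence to read along these lines: *at least 17 subjects per weight group; at least 17 evaluable (mITT) subjects with light and at least 17 with dark pigmentation, Munsell value 6 counting in neither; and at least 40 overall.* State that the pigmentation goal lies within the same 47 enrolled, is not crossed with weight, is not a condition for stopping enrolment, and is an aim that may be missed. Keep running counts from the class already recorded at enrolment.

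2. Restate the Objective 2 power as conditional on achieved group size, labelled *single group, one-sided 0.025, before Hochberg, 14 points, SD 16*: n = 17, 0.92; 16, 0.90; 15, 0.88; 14, 0.86; 12, 0.79; 10, 0.69; 8, 0.57. Add that with 17 in each group the power for both to succeed is about 0.85 if the tests are independent. Without the label and this addition, 0.92 could be read as the power for the whole objective.

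Cost: no added infants, but possibly slower enrolment, and a less favourable stated power. The goal does not guarantee 17 of each. With a 30% dark share of classified infants and 10% intermediate, an expected 17 dark infants would take 17 / (0.9 × 0.3) ≈ 63 evaluable infants, which is why the second change is needed alongside the first.
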